5.8.6. REDUCTION IN CYLINDER POWER

Reduction in cylinder power will be calculated for each eye implanted with the HMTIOL as follows:

$$\text{Cylinder Power Reduction} = \text{absolute value of preoperative magnitude of corneal cylinder (K)} - \text{absolute postoperative magnitude of MRCYL at the corneal plane.}$$

The percent reduction in cylindrical power will be calculated for eyes with non-zero preoperative corneal cylinder as follows:

$$\text{Cylinder Power \% Reduction} = \text{Cylinder Power Reduction} / \text{absolute value of preoperative magnitude of corneal cylinder (K)} \times 100.$$

Descriptive statistics for continuous variables will be used to summarize these outcomes at each visit. [REDACTED]

6. Sample Size

This is a feasibility study and no hypothesis testing will be performed.

The sample size for this study was originally based on refinement of the A-constant (lens power constant). Subsequent developments led to a modification in study design from a multi-center to a single center trial. The sample size was scaled down accordingly to 17 enrolled and treated eyes.

SAP CP-00004

ClarVista Medical, Inc.

7. Analysis Populations

Subjects that are screened but disqualified based on the preoperative and intra-operative eligibility criteria will be excluded from the safety and performance data analyses. However, their reasons for the screen failure will be summarized. The analyses populations are defined below.

7.1.1. SAFETY POPULATION

The Safety Population includes eyes with attempted study lens implantation, (successful or aborted after contact with the eye). The intraoperative and postoperative AEs and DDs will be summarized based on the safety population.

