	
9. Any v sua y s gn f cant ntraocu ar med a opac ty other than cataract n study eye (as determ ned by the nvest gator)
 
10. Uncontro ed g aucoma n study eye (per Invest gator judgement)
 
11. Subjects w th arge refract ve errors (hyperop a/myop a) of ax a or patho og c or g n that, n the op n on of the nvest gator, cou d confound outcomes
 
12. Uncontro ed system c d sease (e.g. d abetes me tus, act ve cancer treatment, menta ness, etc.)
 
13. Subject who, n the c n ca judgment of the nvest gator, s not su tab e for part c pat on n the study for another c n ca reason, as documented by the nvest gator
 
14. Severe dry eye that, n the op n on of the nvest gator, wou d mpa r the ab ty to obta n re ab e study measurements
 
15. Tak ng system c med cat ons that, n the op n on of the nvest gator, may confound the outcome or ncrease the ntraoperat ve and post-operat ve r sk to the subject (e.g. Tamsu os n Hydroch or de – F omax) or other med cat ons nc ud ng ant cho nerg cs, a pha adrenerg c block ng agents w th s m ar s de effects (e.g. sma pup /f oppy r s syndrome)
 
Discont nuat on Cr ter a Dur ng Surgery
 
 1. V treous oss pr or to use of the nvest gat ona dev ce 2. Pos t ve poster or pressure prevent ng safe mp antat on of the ens system 3. Anter or chamber hyphema prevent ng v sua zat on of mp antat on 4. Any zonu ar or capsu ar rupture or capsu ar bag nstab ty 5. Intraoperat ve m os s prevent ng v sua zat on of f xat on features 6. Need for concom tant procedures (e.g. g aucoma surgery, LRI, RK, LASIK, etc.) 7. Subject who, n the c n ca judgment of the nvest gator, s not su tab e for part c pat on n the study for another c n ca reason, as documented by the nvest gator

Planned Analyses
	
All eyes w th attempted study ens mp antat on w be nc uded n the safety analyses. The performance outcomes w be summar zed based on eyes mp anted w th HMTIOL. A data summar es w be performed based on observed data; no mputat on for m ss ng c n ca outcomes w not be performed. [REDACTED]
 
[REDACTED] For cont nuous var ab es, mean, standard dev at on, med an, m n mum, and max mum w be prov ded.

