5.3 ACCOUNTABILITY

The Investigator is responsible for keeping accurate accountability records of the number of study lenses received, dispensed, and returned to Sponsor. The study lenses must be stored under the appropriate conditions in a secure area and are to be implanted on your subjects enrolled in the study, in accordance with the conditions specified in this protocol.

CLARV STA MED CAL

PROTOCOL CP 00004 REV 01

Accountability records will include the following:

- Model and serial numbers
- Receipt date
- Quantities received
- Initials (attributability) of site personnel who received, dispensed, or returned study lenses
- Date of use
- Subject and eye treated with the study lenses (by Subject ID and Initials only)
- Date returned to Sponsor
- Defective or damaged study devices

Periodically throughout the study and/or upon completion, the Sponsor (or designee) will review and verify the Investigator's accountability records. Following verification, and as directed by the Sponsor, unused and explanted products must be returned to the Sponsor.

Note: In addition, any study lenses or components deemed defective, damaged, malfunctioning, or explanted must be retained by the site and returned to the Sponsor for evaluation. Under no circumstances are any components to be discarded or otherwise disposed of. If there is any question as to the applicability of this directive, consult the Protocol Contacts page of this protocol and discuss the situation with a Sponsor representative.

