6.1.4 DEVICE DEFICIENCIES (DD)

A Device Deficiency (DD) is a failure of the device to meet its performance specifications or expectations, or otherwise not perform as intended. This can include either a malfunction or damage to the device or any part thereof, regardless of the source of malfunction or damage, including user error, and regardless of the presence of injury (or lack thereof) to subject, user, or bystander.

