8.2.1 SAFETY POPULATION

The **Safety Population** includes eyes with attempted study lens implantation, (successful or aborted after contact with the eye). The intraoperative and postoperative AEs and DDs will be summarized based on the safety population.

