8.3.1 SAFETY OUTCOMES

8.3.1.1 ADVERSE EVENTS AND DEVICE DEFICIENCIES

Adverse events and device deficiencies will be summarized at each study visit based on the safety population. The number and percentage of eyes reported with the 3-month cumulative and persistent adverse events will be calculated. [REDACTED]

[REDACTED]

[REDACTED]

[REDACTED]

[REDACTED]

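### Device deficiencies are tabulated only on eyes the lens touched, so a lens that fails before contact drops out of the rate when no study lens then reaches that eye

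*SAP*

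**What the plan says.** SAP 7.1.1 defines the analysis set: "The Safety Population includes eyes with attempted study lens implantation, (successful or aborted after contact with the eye". Its next sentence assigns both adverse events (AEs) and DDs to that set. Protocol 8.2.1 uses the same contact rule and says "The intraoperative and postoperative AEs and DDs will be summarized based on the safety population". Protocol 8.3.1.1 repeats it: "Adverse events and device deficiencies will be summarized at each study visit based on the safety population". SAP 5.5 asks for DD rates under the general rules of SAP 5.1 and names no other population. SAP section 2 gives the SAP precedence over the protocol.

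The endpoint itself is defined by the device. Protocol 6.1.4 says "A Device Deficiency (DD) is a failure of the device to meet its performance specifications or expectations, or otherwise not perform as intended". It extends this to damage of any part from any source, "including user error, and regardless of the presence of injury (or lack thereof) to subject, user, or bystander". Protocol 6.3.1 requires sites to report all DDs within 24 hours. Protocol 3.3.2 records those seen before, during or after surgery, and lets the surgeon use a commercial lens when the study lens is not implanted. The accountability records in protocol 5.3 include "Defective or damaged study devices".

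The Planned Analyses entry of the protocol synopsis puts all eyes with attempted implantation into the safety analyses and states no contact condition.

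**The concern.** The DD definition does not depend on the eye, but the analysis set does. A contact rule is sensible for AEs, because an eye that never met the device cannot show the device's effect. It fits DDs less well, because a device can fail in the pack, during loading or in the injector. When such a failure ends the attempt to use a study lens, the event meets the protocol's definition and must be reported, yet the eye is outside the set on which the rate is computed.

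The case is foreseeable. Protocol 4.5 lists damage to the haptic or optic among events that can prevent implantation. It files them under complications unrelated to the device, but 6.1.4 counts damage whatever its source. DD is one of four safety outcomes, the study is small and purely descriptive, and so the tabulated rate is the result.

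**Working it through.** The documents state no DD rate and no expected number of failures, so there is no figure to reproduce. The check has two parts: which eyes enter the rate, and how much one lost eye could move it.

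**Step 1. Trace the eyes under SAP 7.1.1.**

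| What happens | In Safety Population? | Can the DD enter the rate? |
|---|---|---|
| Lens fails before contact; another study lens is implanted | Yes | Yes |
| Lens fails before contact; another study lens touches the eye and is abandoned | Yes | Yes |
| Lens fails after contact | Yes | Yes |
| Lens fails before contact; commercial lens or no lens follows | No | No |

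Only the last route is lost.

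**Step 2. Direction.** Let n be the eyes in the Safety Population, m those with a DD, and k the eyes lost by the last route.

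- Planned rate: m/n
- Rate with the lost eyes restored: (m + k)/(n + k)
- Difference: (m + k)/(n + k) − m/n = k(n − m)/[n(n + k)]

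Because m cannot exceed n, the difference is never negative. Losing these eyes can lower the DD rate or leave it unchanged, but cannot raise it.

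**Step 3. Size.** SAP section 6 gives 17 enrolled and treated eyes. It does not say whether an eye whose lens failed before contact would be among them, so both readings are shown. The values of k and m are assumptions. Intervals are exact (Clopper-Pearson) 95%.

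| Assumption | As planned | Lost eyes restored |
|---|---|---|
| 17 in the set, k = 1, m = 0 | 0/17 = 0% (0 to 19.5%) | 1/18 = 5.6% (0.1 to 27.3%) |
| 17 in the set, k = 1, m = 1 | 1/17 = 5.9% (0.1 to 28.7%) | 2/18 = 11.1% (1.4 to 34.7%) |
| 17 in the set, k = 2, m = 0 | 0/17 = 0% (0 to 19.5%) | 2/19 = 10.5% (1.3 to 33.1%) |
| 17 is the total, k = 1, m = 0 | 0/16 = 0% (0 to 20.6%) | 1/17 = 5.9% (0.1 to 28.7%) |

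One lost eye moves the rate by 5 to 6 percentage points. Check for the second row: 1 × (17 − 1)/(17 × 18) = 16/306 = 5.2 points.

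**Step 4. How likely is at least one such eye?** With an assumed per-eye probability p, the chance in 17 eyes is 1 − (1 − p)^17. It is 15.7% for p = 1%, 29.1% for p = 2% and 58.2% for p = 5%. The documents give no value of p.

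**The case against.** The strongest reply is that nothing is hidden. All DDs reach the sponsor within 24 hours (protocol 6.3.1) and are reviewed on receipt (6.4). Defective devices are logged and returned (5.3). Only one descriptive percentage is affected, no hypothesis is tested, and the intervals above overlap widely. All of that stands: the loss is from the planned summary, not from collection or oversight.

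Second, text is redacted where a remedy might sit: after protocol 8.3.1.1, after SAP 7.1.3, within SAP 5.1 and in two SAP contents entries. A separate DD listing may therefore exist, and its absence cannot be asserted. But the sentences that set the population are visible in SAP 7.1.1 and protocol 8.2.1, and a listing would not change the rate they define.

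A reader might also infer more than the documents support:

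- **That the rate covers only devices that reached the eye.** It does not. A failed lens followed by a second study lens leaves the eye in the set (first two routes in the table).
- **That protocol 6.1.4 itself prescribes 1/18.** It defines an event and sets no denominator. The eighteenth eye is an assumption made for illustration.
- **That several DDs in one eye are collapsed to one.** SAP 5.1 speaks of cases and then of eyes, so a per-eye count is plausible, but no visible text settles it.

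**Conclusion.** The point holds for one route only: a study lens fails before eye contact and no study lens is then implanted in, or touches, that eye. The visible rule removes that DD from numerator and denominator alike, and the removal cannot raise the rate. With about 17 eyes, one such event is worth 5 to 6 percentage points and can be the difference between reporting no deficiency and reporting one. That size rests on an assumed event, since the documents do not say whether any occurred. The effect is confined to the summary of one safety outcome, but it comes from a stated population rule that does not match the protocol's own DD definition or the synopsis. It should be corrected.

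**What to change.** - In SAP 7.1.1 and 5.5, keep the Safety Population for AEs. Summarise DDs over all eyes in which study-lens implantation was begun, or a study lens was prepared on the day of surgery, whether or not the lens touched the eye.
- Add a count and a listing of every DD from the DD Report Forms, showing timing relative to eye contact and whether a study lens was then implanted.
- Reconcile the contact rule with the synopsis wording, which includes all attempted eyes.
- Treat rates per component (base and optic separately) as optional. The accountability records in protocol 5.3 list date of use, eye treated and defective devices, but no field for components opened, so that denominator is usable only if it can be derived.

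The cost is a change of SAP wording and one extra listing. The DD forms are already required. The visible text does not show that they record timing relative to contact, so that item may have to come from the surgical source records. The DD rate may look less favourable. The wider denominator could also take in an eye abandoned before contact without any DD, which would pull slightly the other way: 1/18 = 5.6% instead of 1/17 = 5.9%. The listing makes both cases visible.

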7.1.2. IMPLANTED-EYE POPULATION

The Implanted-Eye Population consists of eyes with successful HMTIOL implantation. Since it is important to evaluate HMTIOL's effect on all study eyes, slit lamp examination, intraocular pressure (IOP), and dilated fundus examination (DFE) will be based on the implanted-eye population.

Additionally, the UCDVA, BCDVA, prediction error, and meridian rotation will be evaluated based on the implanted-eye population.

7.1.3. PER PROTOCOL POPULATION

The Per Protocol (PP) Population contains eyes with successful HMTIOL implantations during surgeries and do not have a major protocol deviation (such as improperly enrolled in the study or lens power calculation errors) and will be considered the primary population for the analysis of performance outcomes. The performance outcomes (UCDVA, BCDVA, and prediction error) will also be evaluated based on the per protocol population.

The protocol deviations will be categorized prior to the analysis.

[REDACTED]

SAP CP-00004

ClarVista Medical, Inc.

8. Interim Analyses

[figure not shown]
There are no plans for formal interim analyses for the purposes of study modification or possible early termination. Any interim analyses will be administrative in nature and results will not be distributed to Investigators or subjects to prevent bias from exposure to accruing study results.

9. Deviations from the Statistical Analysis Plan

Any deviations from the Statistical Analysis Plan will be noted and described with appropriate statistical and clinical rationale as needed. Discrepancies from the Investigational Plan are noted and due primarily to the study design modification from a multi-center to single center trial, without the corresponding amendment to the protocol.

10. References

1. ISO 11979-7:2014 Ophthalmic implants — Intraocular lenses — Part 7: Clinical investigations.
2. Note to File Re: Correction to Appendix A – Table 1: Schedule of Assessments_June 26, 2017

Alcon - Business Use Only

Document: TDOC-0055990

Status: Effective

Effective Date: 24-Apr-2019

Version: 1.0; CURRENT; Most-Recent; Effective
